## VII. PATIENT ENROLLMENT

### INFORMED CONSENT

Patients who are screened and for whom the principal investigator feels would be a good candidate for inclusion in the Mitral TRACER Trial, will be asked to sign the study specific Ethics Committee (EC) approved Patient Information Sheet before any study-specific tests or procedures are performed. Study personnel should explain that even if a patient agrees to participate in the study and signs the Patient Information Sheet, the patient may not be eligible to participate if he/she fails additional eligibility criteria.

A Screening/Enrollment Log will be maintained in the on-site clinical records located at the study site to document select information about candidates who fail to meet the entry criteria.

### ENROLLMENT

Patients will be considered enrolled in the Mitral TRACER Trial once informed consent has been signed and all eligibility criteria confirmed, including intra-operative assessment of suitability of the patient's mitral valve for Harpoon device treatment.

### SCREENING/ PRE-PROCEDURE

**Screening evaluations:** All patients that are identified as potential candidates for the study shall undergo transthoracic echocardiography (TTE) OR TOE. A TOE will be performed at the referring doctor's request or if the Harpoon Medical determines that the TTE images are not readable. Both the TTE and TOE are routine preoperative studies for patients undergoing heart valve surgery.

The screening evaluations will be sent to the Harpoon Medical Patient Eligibility Committee (PEC) who will independently assess the eligibility of the patient for participation in the TRACER study. The PEC will provide the study site with a Pass or Fail for the patient being screened. If the PEC determines a PASS for the patient under consideration, the patient will proceed to the pre-procedure/baseline evaluations. If the PEC determines a FAIL for the patient, the patient will be referred back to the standard of care.

**Pre-procedure/baseline evaluations:** Once the patient is enrolled for the Harpoon Medical procedure, a Physical Assessment will be performed. This includes a comprehensive history and physical examination, including the listing of all medications and dosage. Additionally, the following physical assessments shall be completed:

- Vital signs
- 12-lead ECG
- Routine Laboratory assessment (including WBC count; Hemoglobin; hematocrit; platelet count; creatinine Level, INR)
- Additional Laboratory assessment (including Total Albumin, Total Bilirubin, BNP, NTproBNP)
- A chest radiograph (X-Ray)
- A serum pregnancy test for females with childbearing potential (age < 50 years) shall be completed within 14 days prior to the procedure
- In accordance with the hospital's clinical Standard of Care, a left heart catheterisation (LHC) may be required for all patients >= 45 years of age without risk factors and for any patient with symptoms of coronary artery disease

- Pulmonary Function Tests, when clinically indicated
- 6 Minute Walk test
- Quality of Life Assessment

The data from this physical assessment shall be recorded on a Case Report Form (CRF).

## TREATMENT PROCEDURE/ASSESSMENTS

The procedural approach requires that the patient be administered a general (single lumen) endotracheal anesthesia with appropriate monitoring lines (e.g. arterial line) and heparinised saline to achieve an activated clotting time of  $\geq 350$  seconds. The patient should be placed in the supine position with elevation of the left hemithorax to 30°. Briefly, the procedure consists of performing a small left lateral thoracotomy incision overlying the left ventricular apex, opening the pericardium and selecting an insertion site on the epicardium for the Harpoon Medical device where a monofilament purse-string suture is placed to hold the Harpoon device introducer in place and reduce bleeding. Once the introducer is in place, the device is inserted and positioned adjacent to the mitral leaflet under TOE guidance and bulky suture knot is deployed to secure paired sutures in the leaflet. The paired sutures are brought outside the ventricle. Up to four (4) suture pairs may be placed, using a singled valved introducer, to secure and align apposition between the anterior and posterior mitral leaflets. If more than four (4) suture pairs are required, the valved introducer must be removed and reinserted for reuse, and then an additional four (4) suture pairs may be inserted. Once an adequate number of suture pairs are placed, the device and introducer are removed, and the suture pairs are tightened and secured to the exterior myocardium using pledges for each suture pair. The thoracotomy should be closed, and chest tube(s) should be inserted, per hospital standard of care.

The details of the procedure are described thoroughly in the Harpoon Medical device Instructions for Use.

If in the judgment of the operating surgeon, adequate MR reduction has not been achieved, or if for any other clinical reason, conversion to SOC mitral valve surgery via a median sternotomy shall be performed. This procedure may be performed at the time of the Harpoon Medical TRACER procedure or at a later date/time at the discretion of the operating surgeon. Subjects who undergo a conversion to SOC mitral valve surgery via a median sternotomy will be followed up for 30 days.

## FOLLOW-UP PROCEDURES/ASSESSMENTS

**Post-procedure management:** Standard hospital protocols for the management of patients after mitral valve surgery shall be followed. Unless other indications for anticoagulation are present, all patients shall receive only 325 mg/day, beginning on arrival to the intensive care unit).

**Discharge:** All patients shall be discharged from the hospital at the discretion of the attending cardiac surgeon. Prior to dismissal all patients shall undergo a comprehensive pre-dismissal TOE, as well as a physical assessment (vide supra) in accordance with the schedule of Clinical Investigations.

**Patient follow-up:** Patients shall be seen in the outpatient clinic 30 days (+10 days/-0 days) after the Harpoon procedure. A TTE and a clinical assessment shall be performed at that time (in accordance with the schedule of Clinical Investigations) to evaluate the device against the primary and secondary performance and safety endpoints.

Additional clinical and TTE follow-up in a registry fashion shall occur for all active subjects (in accordance with the Clinical Investigations defined in the table below) at the following intervals:

- 6 months (+/- 30 days),
- 12 months (+/- 30 days)
- 18 months (+/- 30 days)
- 24 months (+/- 30 days)
- 30 months (+/- 30 days)
- 36 months (+/- 30 days)
- 48 months (+/- 30 days) and
- 60 months (+/- 30 days)

If due to an increase of MR, or due to any other medical circumstances, and a study patient has to undergo a Mitral Valve reoperation, this patient will be followed up by the study team for 30 days and then will be exited from the study

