- Open-heart operations to repair or replace the mitral valve. Open cardiac mitral valve operations either require a sternotomy or a thoracotomy, cardiopulmonary bypass, aortic manipulation and cardioplegic cardiac arrest. Mitral valve repair is carried out with leaflet resectional techniques (Carpentier) or nonresectional techniques using ePTFE chordae tendineae placed under direct vision. Because the heart is flaccid and arrested, sizing the chordae tendineae is difficult. Improper sizing of the chordae tendineae may result in a failed or ineffective mitral valve repair. The success of mitral valve repair is significantly dependent on the expertise of the operating surgeon. For patients with degenerative mitral valve disease, mitral valve replacement is inferior to mitral valve repair (short-term higher perioperative mortality and long term substantially higher risks of stroke and prosthetic valve endocarditis as well as either the need for lifelong anticoagulation (mechanical valve) or the risk of repeat mitral operation (bioprosthetic valve)). Mitral valve replacement (compared to repair) is a risk of open cardiac surgery. This procedure is also very invasive and not a feasible option for all patients.
- In 2008, Evalve received a CE mark for the MitraClip in the EU. Shortly thereafter, the company was acquired by Abbott Labs. The implantation of MitraClip does not involve open-heart surgery, but mimics the surgical method of edge-to-edge valve repair where the mitral valve leaflets are clipped together with the device instead of being sutured together. Extensive clinical experience with the MitraClip has been collected over the last six years and the clinical efficacy has been mixed.

 <http://www.rbhh-specialistcare.co.uk/diagnosis-treatments/heart-treatments/valve-repair-or-replacement-incl-tavi-mitral-valve-repair/>

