#### PATIENT WITHDRAWAL FROM THE STUDY

A withdrawal refers to a patient who is determined to be inactive in the study due to physician discretion, patient or family choice (if the patient becomes incapacitated and is unable to continue with the study due to a family choice), and loss to follow-up or patient death. Final status shall be reported on all patients as per the informed consent. Three documented phone calls and a registered/certified letter shall be used to assure that there is minimal loss to follow-up. If these efforts to contact the patient are unsuccessful, the patient shall be considered lost to follow-up.

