The hypotheses for the primary performance endpoint can be rewritten as:

$$H_0: \pi_{\text{Harpoon\_performance}} \leq \text{HC \%}$$

$$H_A: \pi_{\text{Harpoon\_performance}} > 58\%$$

To achieve 90% power using a two-sided  $\alpha$  of 0.05 (one-sided 0.025), the sample size was estimated based on a single sample compared to a constant (0.58). Based on this calculation, 26 patients are required to demonstrate non-inferiority. To adjust for patients lost to follow-up, we have decided to enroll up to 30 patients in the TRACER Trial. Moreover, 30 patients has been a sufficient number of patients to provide a satisfactory profile of the adverse events likely to occur with beating heart mitral valve repairs in the aforementioned studies. Last, 30 patients is consistent with the sample size of previous beating heart, mitral valve repair devices. For example, the CE mark trial of the NeoChord DS1000 was conducted in 30 patients.

These data from these 30 patients shall be used to assess the safety and performance of the device when used on a human patient. All data shall be captured on an intent-to-treat basis. Data shall be reported as descriptive statistics.

The percentage of patients with improvements in MR reduction at the conclusion of the procedure, at the time of the hospital dismissal and at 30 days, six months, one, two, three, four and five years will be assessed. Specifically the percentage of patients that demonstrate MR reduction from “severe” to less than or equal to “moderate” at the conclusion of the procedure and at 30 days. While the number of subjects missing the primary endpoint of improvement in MR is anticipated to be small, if any, the following algorithm will be used to impute missing observations:

- Subjects who die prior to evaluation at 30 days or fail the procedure will be considered failures for the primary analysis.
- Patients lost after the procedure for other reasons will have their last observation carried forward (from procedure to 30 days). Should this situation occur, an additional sensitivity analysis, a tipping point analysis, will be conducted whereby each subject missing 30 day follow-up will be counted as a failure in succession, and the number of subjects with

missing data imputed as failures which “tip” the analysis to non-significance will be reported.

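### The analysis plan does not say how late MR status is counted after a repeat mitral procedure, so the one- to five-year durability percentages can be too high

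*Combined protocol and SAP*

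**What the plan says.** Two rules in Section VII limit follow-up after further mitral treatment. Under Treatment Procedure/Assessments: "Subjects who undergo a conversion to SOC mitral valve surgery via a median sternotomy will be followed up for 30 days". Under Follow-up Procedures/Assessments the trigger reads "and a study patient has to undergo a Mitral Valve reoperation", with the consequence that "this patient will be followed up by the study team for 30 days and then will be exited from the study". Neither rule mentions a catheter procedure, and reoperation is not defined.

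Everyone else continues: "Additional clinical and TTE follow-up in a registry fashion shall occur for all active subjects", with visits to 60 months. The withdrawal paragraph in Section VI begins "A withdrawal refers to a patient who is determined to be inactive in the study due to physician discretion" and goes on to patient or family choice, loss to follow-up and death. A second mitral device is not on that list.

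The MR assessment in Section X opens with "The percentage of patients with improvements in MR reduction at the conclusion of the procedure, at the time of the hospital dismissal and at 30" (the quote breaks off at the 30-day visit). The list then runs on to the half-year visit and to yearly assessments through year five. The only failure rule in Section X concerns the 30-day analysis: "Subjects who die prior to evaluation at 30 days or fail the procedure will be considered failures for the primary analysis". What it means to fail the procedure is not defined. For later visits there is no failure rule and no instruction on echoes taken after another mitral procedure.

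The secondary performance endpoint (Sections II and IV) is MR severity at 6 to 36 months. The four- and five-year assessments appear only in Section X.

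**The concern.** A late echo is informative about the Harpoon repair only if that repair is what is being imaged. After a second mitral procedure the reading describes the combined result. Where a second procedure was done because MR had returned, the repair has already failed for performance purposes.

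The plan provides for neither situation. A reoperated patient leaves the study, so the failure is missing from every later percentage. A patient treated by catheter meets neither exit trigger as worded and may have later echoes that look good because of the other device. Two patients with the same recurrence could then appear as an absence and as an improvement, with neither appearing as a failure.

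The possibility is visible from the protocol itself. Its background section describes a marketed catheter device for MR: "The implantation of MitraClip does not involve open-heart surgery". Section X names that device as one of two reference devices for degenerative MR in the EU. At stake are the late MR percentages, which are the performance output of the extended follow-up.

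**Working it through.** **The plan's own figures.** The documents give no figure for late MR, for reinterventions or for the number of late echoes, so there is nothing to reproduce on this point. The nearest computed figure is the 26 patients for the 30-day test against 58%. Its assumed Harpoon success rate is not stated. A rate of 0.86 (my assumption) gives ((1.96·√(0.58·0.42) + 1.2816·√(0.86·0.14)) / 0.28)² = 25.4, rounded up to 26. Nothing below depends on it.

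**Inputs (assumed unless sourced).** N is the number treated: 30 is the CE-mark cohort in Section X, and 80 is the ceiling implied by Section II (up to 20 patients in each of up to four countries, 20 × 4). Let r be the patients with recurrent MR who had a repeat mitral procedure, and s the patients at or below moderate MR without one. Take s = 24 of 30, full echo attendance otherwise, and MR at or below moderate after any catheter procedure.

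**Three ways to count the same patients at a later visit.**
- All r reoperated and exited: s / (N − r)
- All r treated by catheter and kept: (s + r) / N
- All r counted as failures and kept: s / N

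| r | Exited | Kept, post-device echo used | Counted as failure |
|---|---|---|---|
| 1 | 24/29 = 82.8% | 25/30 = 83.3% | 24/30 = 80.0% |
| 2 | 24/28 = 85.7% | 26/30 = 86.7% | 24/30 = 80.0% |
| 3 | 24/27 = 88.9% | 27/30 = 90.0% | 24/30 = 80.0% |

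The excess is r/N by the catheter route and (s/N)·r/(N − r) by the exit route. For r = 3 these are 3/30 = 10.0 points and 0.80 × 3/27 = 8.9 points. Both run in the same direction and are of similar size. Per patient, the catheter route is 1/30 = 3.3 points or 1/80 = 1.25 points. With r = 0 there is no effect.

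**Reach into the 30-day test.** Assuming an exact binomial test of 58% at one-sided 0.025 with 30 patients, 24 successes are needed (24/30: p = 0.0099; 23/30: p = 0.0269). One reclassified patient would change the conclusion only if the count stood exactly at 24 and the reintervention preceded the 30-day echo. A reintervention after the 30-day visit cannot affect that test.

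**The case against.** The strongest reply is that the plan is silent here, and that silence is not a wrong rule. A reader might infer that a patient treated by catheter must stay active and is then scored as a Harpoon success. The documents state neither. A site could take reoperation to include a catheter procedure, physician discretion is a listed route to inactive status, and no text says how an echo after a second device is classified. The threshold of at most moderate MR is specified only for the end of the procedure and for 30 days; later readings are tracked and reported descriptively.

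Four further inferences also lack support:
- That late MR to 60 months is the secondary endpoint. That endpoint stops at 36 months.
- That bias would differ by site according to access to catheter therapy. Nothing in the documents bears on this.
- That such cases occurred. None is reported, and the fallback the protocol describes is conventional open surgery in patients who were referred for surgery.
- That the event would go unrecorded. Adverse events are collected through 60 months with the intervention described, and a hospitalised reintervention would probably meet the SAE definition.

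These points remove any claim of a certain or measured bias. They do not close the gap. Nothing links an adverse event record to MR status, and committee adjudication ends at 36 months. Capturing data on an intent-to-treat basis does not classify a reading. Reading reoperation broadly would move the catheter-treated patient from the numerator route to the exit route, which also overstates durability.

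**Conclusion.** The gap stands in limited form. Section X has no rule for MR status after any mitral reintervention, surgical or catheter. Followed as written, an exited reoperated patient leaves later denominators, and a catheter-treated patient could add a post-device echo to the numerator. Either would raise the descriptive MR percentages at 6 to 36 months and at four and five years.

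The size cannot be known from the documents. On assumed counts of one to three patients in 30, the excess is about 3 to 10 points; in a cohort of 80, one catheter-treated patient adds 1.25 points. These figures assume complete echoes otherwise and a good result after the second device. The 58% test is largely untouched. The change should be made because it is cheap and the direction of error is the same by both routes, although how often it arises is uncertain.

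**What to change.** Amend Section X only, with text to this effect:

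- Mitral reintervention means any repeat mitral procedure after the Harpoon procedure, surgical by any access or transcatheter.
- MR readings after a reintervention are not used as evidence of Harpoon performance.
- From the date of reintervention the patient counts as a performance failure and stays in the denominator at every later visit, including after exit from the study.

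Before the one- to five-year tables are produced, search the existing SAE and AE records for such procedures and their dates. After 36 months this means site-reported records. Show the number of reintervention failures beside each percentage.

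Leave the Section VII follow-up and exit rules unchanged for this purpose. They govern follow-up, and widening the exit trigger could lose late data without settling how MR is counted.

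The cost is a few sentences and a check of a small database. Late MR success may be slightly lower. A reintervention for a reason other than recurrent MR would also count as a failure. Reintervened patients would stay in the denominator while patients lost for other reasons may not, which is why the counts should be shown.

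### Late MR percentages (6 months to 5 years) have no stated denominator or failure rule; computed on available echoes, they would leave out converted and re-operated patients and overstate device success

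*Combined protocol and SAP*

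**What the plan says.** **Late analysis.** Section X, Statistical Analysis, plans the share of patients whose MR has improved at the end of the procedure, at dismissal, at 30 days, and then at "six months, one, two, three, four and five years will be assessed". The sentence that defines a responder begins "Specifically the percentage of patients that demonstrate MR reduction from" and ties the change from severe to moderate or less to two time points only, the end of the procedure and 30 days. The secondary performance endpoint in Section IV says only that late MR severity is recorded.

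**Counting rules.** Section X states: "Subjects who die prior to evaluation at 30 days or fail the procedure will be considered failures for the primary analysis". Carry-forward runs from the procedure to 30 days, and the tipping-point analysis concerns missing 30-day data. Nothing comparable is given for later visits. Section X also says that data are captured on an intent-to-treat basis, without defining that set.

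**Who is still under echo.** In Section VII, Follow-up Procedures/Assessments: "Additional clinical and TTE follow-up in a registry fashion shall occur for all active subjects". A mitral reoperation there may arise "If due to an increase of MR, or due to any other medical circumstances", and afterwards "this patient will be followed up by the study team for 30 days and then will be exited from the study". Under Treatment Procedure/Assessments, one stated ground for conversion to open surgery is that "adequate MR reduction has not been achieved", and "Subjects who undergo a conversion to SOC mitral valve surgery via a median sternotomy will be followed up for 30 days".

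**Conflicting statements.** The Follow-up entry of the Study Summary (Section II), Number of Patients (Section VI) and the opening of Section X each say that all patients are followed to 60 months.

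**The concern.** The Study Summary gives extension to five years as the purpose of this amendment, and the late MR percentages are its main performance output. Under the Section VII rules, loss of late echo data is linked to the outcome: a repair that fails and leads to conversion or reoperation takes the patient out of late echo follow-up after 30 days. A percentage computed on whoever has an echo would then describe mainly the repairs that held. Read as device success over time, it would be too high.

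The Study Summary also says that follow-up already ranges from 6 to 36 months. Some late data may therefore exist before the denominator has been fixed, which is a reason to settle the rule now and show both rates.

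**Working it through.** The plan states no late MR rate, no count of conversions or reoperations and no late denominator, so there is no figure of its own to reproduce. The check is to set the rules side by side and then size the gap under stated assumptions.

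**Step 1: is a converted or re-operated patient given a late outcome?**
- Failure rule: primary analysis only, to 30 days. No late outcome.
- Carry-forward and tipping point: to 30 days. No late outcome.
- Intent-to-treat sentence: concerns data capture. It does not say how a patient without an echo is counted.
- Late echo: active subjects, with 30 days of follow-up after conversion or reoperation. No scheduled study echo under these rules, although three other places say all patients are followed to 60 months.

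The late percentage is therefore undefined for these patients.

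**Step 2: the formula.** Let N be patients enrolled, k those converted or re-operated and without a late echo, and s the successes.
- Rate on available echoes: s/(N-k).
- Rate with the k counted as failures: s/N.
- Ratio: N/(N-k). Gap: observed rate × k/N.

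This ratio is exact only if all k count as failures and nobody else is missing. With m others missing, it becomes (N-m)/(N-m-k) if they are left out of both rates, or N/(N-k-m) if they also count as failures. For N=30, k=3, m=2 these are 28/25 = 1.12 and 30/25 = 1.20.

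**Step 3: size.** N=30 is the CE-mark cohort in Section X. The values of k and s are assumptions.

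| k | Available echoes | k counted as failures | Gap (points) |
|---|---|---|---|
| 0 | 27/30 = 90% | 27/30 = 90% | 0 |
| 1 | 26/29 = 90% | 26/30 = 87% | 3 |
| 2 | 25/28 = 89% (exact 95% CI 72–98%) | 25/30 = 83% (65–94%) | 6 |

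The gap depends on k/N, so a larger cohort with the same event proportion has the same gap.

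**Step 4: does the failure-counted rate have its own problem?** Yes, if its denominator is patients with an echo plus prior failures. Suppose 30 patients, 4 prior failures and 26 lasting successes: 26/30 = 87% at 36 months. If 10 of the 26 do not re-consent to years 4 and 5, the rate becomes 16/20 = 80%, a 7-point fall with no valve changed. Bounds over all enrolled patients run from 16/30 = 53% to 26/30 = 87% and show that the fall may be due to missing data. This is why neither rate should stand alone.

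**The case against.** The strongest reply is that late MR is secondary, descriptive and collected in a registry manner, and that an observed-case grade shown with its n is a valid description of the patients still under echo. That stands. It limits the point to how the percentage is read; a descriptive percentage still needs a defined numerator and denominator.

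Second, these failures do not disappear from the report. A mitral reoperation would normally meet the SAE definition in Section VIII, and Section X counts patients with AEs or SAEs at every visit to 60 months. That also stands, except that the table does not separate reoperation from other events.

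Third, the intent-to-treat wording may point towards all enrolled patients as the denominator. It may, but it assigns no outcome to a patient without an echo.

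Fourth, the size is unknown. No value of k is given, not every conversion or reoperation is for MR, and enrolment requires intra-operative confirmation of suitability, so patients found unsuitable at that stage are outside N. All of this stands.

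A reader might go further and infer that the plan itself produces a rise from 30 days to 6 months: with 2 conversions and 25 unchanged successes, 25/30 = 83% becomes 25/28 = 89%. The documents do not support that as a finding. It needs procedural failure to include conversion, which is not defined, and a 6-month denominator of available echoes, which is not stated. Nor does the protocol call converted patients exited. It uses that word only for reoperation and gives converted patients 30 days of follow-up.

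**Conclusion.** The point holds in a conditional form. Section X plans MR percentages to five years without a late denominator, responder definition or failure rule, while the Section VII rules end echo follow-up for patients whose repair failed and led to conversion or reoperation. If available echoes are used, the late rate overstates device success by N/(N-k), provided all k count as failures and nobody else is missing. For N=30 that is nothing at k=0, about 3 points at k=1 and about 6 points at k=2, at roughly 90% observed success; these counts are hypothetical.

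It would be wrong to conclude that late results will be inflated by a known amount, since neither k nor the denominator is stated. The 30-day primary result is unaffected. Settling the matter is a cheap improvement to the analysis plan.

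**What to change.** Analysis wording only, at the late visits that Section X lists:

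- (a) State whether severe to moderate or less is also the late responder definition.
- (b) Report the observed-case rate with its n. Beside it, report a rate in which prior conversion and mitral reoperation count as failures, and list the reason for each event.
- (c) Always show the second rate with best- and worst-case bounds over all enrolled patients, because it falls spuriously when non-failed patients are missing or do not re-consent (Section VIII, Retrospective Collection of Data).
- (d) Show deaths and missing patients as separate counts, with a sensitivity analysis that counts deaths as failures. Counting all deaths avoids the need for a cause-of-death classification in years 4 and 5, when committee adjudication has ended.
- (e) Optionally, add the cumulative incidence of conversion or mitral reoperation, with numbers at risk.

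Separately, reconcile the statements that all patients are followed to 60 months (Sections II, VI and X) with the 30-day limits after conversion and reoperation in Section VII. Which follow-up rule applies is for the sponsor and investigators to settle.

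Cost: a little more analysis and one table, with no extra visits. The downside is that late success rates may look lower.
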